8.2 Adverse events

8.2.1 Data considerations

Adverse events will be recorded from the time of informed consent until study completion. All AEs will be coded as described in [Section 3.8](#).

In addition, AEs will be classified according to the Common Terminology Criteria for Adverse Events (CTCAE) Version 5 or later for severity. For any AEs where it is not possible to provide a CTCAE grading, the events will be assessed using a standard intensity classification (mild, moderate and severe). For the purpose of reporting severe AEs, all CTCAE severity classifications will be mapped to a standard intensity classification as described below:

- Grade 1 - Mild

- Grade 2 - Moderate
- Grade 3, 4, 5 - Severe

These will be tabulated together with the AEs that were not classified according to CTCAE criteria (i.e., all Grade 1 AEs as per CTCAE criteria will be included in the ‘mild’ category together with those AEs classified as mild as per the standard intensity classification). In the case a mapped standard intensity classification per above rule is different from the standard intensity classification on CRF, the worst case will be used as the standard intensity classification (i.e. an AE with Grade 1 and moderate as intensity classification will be classified into moderate).

A TEAE is defined as an AE starting on or after the time of first administration of IMP in MG0004 or any unresolved event already present before the first administration of IMP in MG0004 that worsens in intensity following exposure to IMP in MG0004, up to and including 8 weeks (56 days) after the end of the Treatment Period or 8 weeks after the last of IMP in study participants who discontinue the study or IMP.

A persistent AE is defined as an unresolved AE that extends continuously from MG0003 to MG0004 and does not worsen in intensity following exposure to IMP in MG0004. Persistent AEs will be recorded in MG0004 database and as other non-TEAEs will be listed only.

Where dates are missing or partially missing, AEs will be assumed to be treatment-emergent unless evidence exists that does not allow the AE to be treatment-emergent. Handling of missing dates for classification of AEs as TEAEs is described in [Section 4.2.2](#).

The following rules will be used to assign a TEAE to a study period:

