Individual study participants will be assessed for ADA participant status, composed of 6 categories: ADA negative, inconclusive, and ADA positive, whereby a positive participant’s status is determined as originating from a treatment-induced, boosted, reduced or unaffected ADA response.

Study participants who are identified as being treatment-induced or treatment-boosted ADA-positive will be grouped as treatment-emergent (TE)-ADA positive participants. Study participants who are identified as being treatment-reduced or treatment-unaffected ADA-positive will be grouped as non-TE-ADA positive participants. Both TE-ADA positive and non-TE-ADA positive participants will be further classified as NAb negative or NAb positive.

The individual and combined ADA participant categories will be derived and summarized through each of the scheduled sampling points (ie Week 5, 9, 21, 33, 45, 52 and 60) and EOS visit, unless specified otherwise.

Table 10-1: Terms and Definitions for ADA Status Evaluation in Study Participant

Classification	Classification Label	Definition
Individual participant categories		
1	Pre-ADA negative – treatment induced ADA negative (ADA-NEG)	Study participants who have an ADA negative sample at Baseline and at all sampling points post-Baseline up to the timepoint of interest.
2	Inconclusive	Study participants who have an ADA positive or negative Baseline sample and some post-Baseline samples are missing or inconclusive, while other post-Baseline samples are ADA negative up to the timepoint of interest.
3	Pre-ADA negative – treatment induced ADA positive (TI-POS)	Study participants who have an ADA negative sample at Baseline and have at least one ADA positive sample at any sampling point post-Baseline up to the timepoint of interest.
4	Pre-ADA positive – treatment boosted ADA positive (TB-POS)	Study participants who have an ADA positive sample at Baseline and at least one ADA positive sample at any sampling point post-Baseline up to the timepoint of interest, with increased titer values compared to Baseline (greater than a predefined fold difference increase from Baseline value which will be defined within the validation of the assay i.e. MSR of the assay).

5	Pre-ADA positive – treatment reduced ADA positive (TR-POS)	Study participants with an ADA positive sample at Baseline, and ADA negative samples at all sampling points post-Baseline up to the timepoint of interest.

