10.3.2 ADA summaries

The following outputs will be presented on the SS.

Tables:

- Number and percentage of participants with ADA (positive, negative, inconclusive, missing) and NAb (positive, negative, missing) sample status at the time of each visit will be summarized by first dose received and RLZ total. Denominator is the number of study participants having a non-missing result at that visit.
- Number and percentage of participants in each of the individual and combined ADA participant status categories presented in [Table 10-1](#) will be summarized by first dose received and RLZ total at each scheduled visit and EOS visit. The table will be repeated by prior treatment in MG0003 (RLZ total or placebo) up to Week 9.

- Total prevalence of pre-existing ADA and NAb, defined as number and percentage of participants having an ADA positive sample status at baseline, with the denominator being the total number of study participants having an evaluable sample result at baseline. Missing samples will not be included in the denominator. The table will be repeated by prior treatment in MG0003 (RLZ or placebo). The same will be repeated for NAb.
- The first occurrence of treatment-emergent ADA positivity: cumulative number and percentage of TE-ADA positive participants (category 7) who are ADA positive for the first time at each visit. The table will be repeated by prior treatment in MG0003 (RLZ or placebo).
- Summary table of mean maximum percentage CFB in total IgG and mean CFB in MG-ADL, summarized by ADA participant categories 1, 2, 9, 10, 11 and 12 for the corresponding time period of interest and by treatment group and RLZ total [REDACTED].
- Overall summary table of TEAEs at Week 9 and EOS summarized by ADA participant categories 1, 2, 7 and 8 for the corresponding time period of interest.
- Summary of incidence of TEAE at Week 9 and EOS by ADA participant category 1, 2, 7 and 8 for the corresponding time period of interest.
- Summary table of AEOF hypersensitivity reactions, anaphylactic reactions and infusion reactions at Week 9 and EOS by ADA participant category 1, 2, 7 and 8 for the corresponding time period of interest.

Figures:

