- Individual time course plots for ADA positive study participants with at least one ADA positive sample, representing ADA and NAb titers (on log-scale), percentage CFB for total IgG and MG-specific autoantibodies, and CFB for MG-ADL total score. The sub-title of the graph will include the study participant number, bodyweight category, treatment group (including prior treatment group in MG0003), and individual ADA participant category (3, 4, 5, 6) up to EOS. The dosing will be represented in the x-axis with bars/arrows at the time of dose.
- Spaghetti plots of individual time course of ADA titer for ADA positive participants in categories 9, 10, 11 and 12 (determined through EOS), whereby all categories are overlaid on the same plot and visualized using different symbols and colors. The ADA titer results will be presented on a log-scale. Dosing time points should be indicated below the x-axis. The same plot will be repeated for NAb titer for NAb positive participants in categories 9 and 11.
- A box-and-whisker plot of maximum postdose ADA titer (on log-scale) through Week 5, Week 9, Week 52 and EOS versus ADA participant category for categories 9, 10, 11 and 12 (determined for the corresponding time period of interest). The same plot will be repeated for NAb titer for ADA participant categories 9 and 11.
- Time course plot of mean CFB in MG-ADL total score, summarized by ADA participant category 1, 2, 9, 10, 11 and 12. Categories will be determined for the time period from baseline up to timepoint of interest (Week 5, 9, 52 and EOS). Separate plots for each treatment group and RLZ total [REDACTED].

- Spaghetti plots of individual time course of percentage CFB for total IgG, for each of the ADA participant categories 1, 2, 9, 10, 11 and 12 and time period of interest (Baseline up to Week 5, Week 9, and EOS) whereby the ADA participant categories are multipaneled. Separate plots for each treatment group and RLZ total [REDACTED]. Individual samples that tested positive for ADA will be visualized using a symbol and/or color. Dosing time points should be indicated below the x-axis.
- Scatter dot plot of individual CFB in MG-ADL total score categorized by ADA titer tertile (including category ADA not present) for each scheduled assessment (Week 5, 9, 21, 33, 45, 52, and 60). The same plot will be repeated for NAb titer.

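### The safety-by-ADA tables count every TEAE since the first MG0004 dose under an ever-positive label, so for treatment-induced positives, events before the first positive sample dilute any ADA effect

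*SAP*

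**What the plan says.** SAP 10.3.2 lists three safety-by-ADA tables. The first is "Overall summary table of TEAEs at Week 9 and EOS summarized by ADA participant categories 1, 2, 7 and 8". The second gives TEAE incidence by the same categories. The third is "Summary table of AEOF hypersensitivity reactions, anaphylactic reactions and infusion reactions at Week 9 and EOS", again by categories 1, 2, 7 and 8.

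Category 7 (treatment-emergent positive) combines categories 3 and 4 of SAP Table 10-1. Category 3 participants are ADA negative at Baseline and "have at least one ADA positive sample at any sampling point post-Baseline up to the timepoint of interest". Category 4 participants are already positive at Baseline, as are categories 5 and 6, which form category 8. Status is derived through "the scheduled sampling points (ie Week 5, 9, 21, 33, 45, 52 and 60) and EOS visit". For the MG-ADL plot the window is explicit: "Categories will be determined for the time period from baseline up to timepoint of interest". The safety tables refer only to the matching period.

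SAP 8.2.1 sets the start of the event window: "A TEAE is defined as an AE starting on or after the time of first administration of IMP in MG0004". Nothing in 10.3.2 limits events to those after ADA was found, splits them by onset, or adjusts for exposure.

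For participants given rozanolixizumab in MG0003, SAP 3.3 and 10.3.1 place the ADA Baseline in MG0003 and leave MG0003 post-baseline samples out of MG0004 status.

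**The concern.** The label can be fixed by a sample taken after the event it is used to classify. A category 3 participant with an infusion reaction in Week 10 and a first positive sample at Week 45 appears in the EOS table as an ADA-positive participant with a reaction. Time and events from the negative period are mixed into the positive column, which pulls a true ADA-related increase towards no difference.

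These tables are the planned comparison of safety by ADA status, including the reactions for which an ADA link is of most interest. A diluted contrast could reassure falsely.

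The SAP already applies the right principle to another status that changes over time: SAP 8.2.2 assigns each TEAE to the most recent dose level before onset. ADA status gets no such rule. No other ADA output fills the gap. First positivity is tabulated by visit without AE onset, and the individual time-course plots and the by-subject ADA listing carry no AEs. The only onset graph (SAP 8.2.3) covers headache relative to infusion.

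A second problem is follow-up. Participants may leave for MG0007 after 6 visits (Protocol 4.1), against a maximum of 60 weeks (Protocol 4.4), and the tables show crude percentages.

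**Working it through.** The documents give no ADA effect, event rate or conversion-time distribution, so there is no planned figure to reproduce. The check uses only the sampling weeks in SAP 10.3.1.

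**Inputs.** Elapsed time is week minus 1. Post-Baseline samples at Weeks 5, 9, 21, 33, 45, 52 and 60 fall at 4, 8, 20, 32, 44, 51 and 59 elapsed weeks. The event window is T = 8 for the Week 9 table and T = 59 for the EOS table. I read both tables as cumulative from the first MG0004 dose; this follows from the TEAE definition, and no text says otherwise.

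**Assumptions.** Constant background event rate, equal follow-up, true rate ratio RR = 2 once ADA is present.

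**Formulas.** Let f be the share of the window before ADA. Its low value dates ADA at the last negative sample and its high value at the first positive sample.
- Observed rate ratio = 1 + (1 - f)(RR - 1)
- Share of events before ADA = f / [f + RR(1 - f)]

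| Table | First positive | f | Observed ratio, true RR 2 |
|---|---|---|---|
| Week 9 | Week 5 | 0/8 to 4/8 = 0-50% | 2.00-1.50 |
| Week 9 | Week 9 | 4/8 to 8/8 = 50-100% | 1.50-1.00 |
| EOS | Week 5 | 0/59 to 4/59 = 0-7% | 2.00-1.93 |
| EOS | Week 9 | 4/59 to 8/59 = 7-14% | 1.93-1.86 |
| EOS | Week 21 | 8/59 to 20/59 = 14-34% | 1.86-1.66 |
| EOS | Week 33 | 20/59 to 32/59 = 34-54% | 1.66-1.46 |
| EOS | Week 45 | 32/59 to 44/59 = 54-75% | 1.46-1.25 |
| EOS | Week 52 | 44/59 to 51/59 = 75-86% | 1.25-1.14 |
| EOS | Week 60 | 51/59 to 59/59 = 86-100% | 1.14-1.00 |

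Share of events before ADA in the EOS table, dated at the first positive sample, RR 2: Week 9, 8/(8 + 2×51) = 7%; Week 33, 32/(32 + 2×27) = 37%; Week 45, 44/(44 + 2×15) = 59%.

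**Sensitivity to event timing.** Suppose half of background events fall in the first 8 weeks (an assumption; RR 1). The pre-ADA share at EOS is then 0.5 + 0.5×(t - 8)/51 for t of 8 weeks or more: 50% for Week 9 (t = 8), 62% for Week 21 (t = 20) and 74% for Week 33 (t = 32).

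**Follow-up.** Suppose there is no ADA effect and a 59-week risk of 20% (an assumption). The weekly rate is -ln(0.8)/59 = 0.00378. A group followed for 59 weeks shows 20.0% and one followed for 20 weeks shows 1 - exp(-0.00378×20) = 7.3%. Whichever group is followed longer looks worse.

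**The case against.** ADA is among the other objectives (SAP 2.1.3), and everything is descriptive with no testing (SAP 4.1, 4.6). First positivity by visit, the by-subject ADA listing and the AE-of-focus listings allow reactions to be dated against ADA case by case. This lowers the priority. It does not correct the tables, because the link would have to be made by hand.

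The objection also limits scope, and that part stands. Three stronger readings are tempting.

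- A reader might infer that most events in the ADA-positive column precede ADA. The documents give no conversion times. If equal numbers first turned positive at each visit (an assumption), the average pre-ADA share of the EOS window would be 159/413 to 218/413, or 39-53%, depending on how ADA is dated. For Week 5 and Week 9 converters it is at most 14%.
- A reader might infer that every reaction in Weeks 1-4 precedes treatment-emergent ADA, because the first post-Baseline sample is at Week 5. Participants given rozanolixizumab in MG0003 may enter already positive, and Protocol Table 1-1 schedules an ADA sample at Visit 1. Categories 4, 5 and 6 are Baseline positive by definition.
- A reader might infer that never-positive participants who transfer early fall outside category 1. ADA is sampled at PEOT (Protocol Table 1-1), and PEOT data map to the next scheduled assessment (SAP 3.2.3), so a participant with only negative samples could be category 1. The SAP does not settle this.

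**Conclusion.** The point holds for treatment-induced positives, category 3 within category 7. Their events before the first positive sample are counted as ADA-positive events, and a true effect is diluted. At a constant event rate and equal follow-up, the dilution at EOS is small for early converters (a ratio of 2 shows as at least 1.86) and material for later ones (1.66-1.46 at Week 33, 1.46-1.25 at Week 45). In the Week 9 table, those first positive at Week 9 would show 1.50-1.00. How much the whole column is affected cannot be stated, because it depends on when ADA appears. Front-loaded events would raise the pre-ADA share, but the documents do not give event timing either. Unequal follow-up is a separate bias of unknown direction.

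**What to change.** Keep the three tables in SAP 10.3.2 and add the following.

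- For category 3 only, split events by onset before versus on or after the first ADA-positive sample. A split across all of categories 7 and 8 would not work: category 5 has no post-Baseline positive sample to date from.
- Use the MG0004 Visit 1 sample to identify participants pretreated with rozanolixizumab who are already positive at entry, and count their time as ADA positive from the first MG0004 dose. State this use explicitly, because Visit 1 is also the last MG0003 visit and SAP 10.3.1 sets MG0003 post-baseline samples aside.
- Add exposure-adjusted rates. ADA-negative time is category 1 time plus category 3 time before first positivity. Show Baseline-positive participants (categories 4, 5 and 6) separately, not in ADA-negative time.
- Add a sensitivity version that starts positive time the day after the last negative sample.
- Add AE-of-focus onset markers to the individual time-course plots already planned.

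The cost is SAP wording and some extra programming on data already collected. The remaining limit is that conversion is dated only to the sampling interval, up to 12 weeks, which the sensitivity version brackets.

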10.4 Immunology

All analyses described in this section will be based on the SS.

10.4.1 Serum complement levels and plasma complement levels

Serum (C3 and C4) and plasma (C3a and C5a) complement variables will be listed by treatment group, visit and time point including changes from Baseline. Descriptive summaries will be presented for both absolute values and changes from Baseline for participants who experience a severe headache, infusion reaction or hypersensitivity reaction. The Baseline values are defined as [Section 3.3](#).

Measurements BLQ will be imputed with half of the LLOQ for the purpose of calculating change from Baseline. Measurements above the limit of quantification (ALQ), if applicable, will be imputed to the upper limit of quantification.

Serum and plasma complement results will be listed.

10.4.2 Cytokines

Cytokines will be summarized by treatment group, visit and time point for both absolute values and changes from Baseline for participants experiencing with severe headache, infusion reactions or hypersensitivity reaction. The Baseline values are defined as [Section 3.3](#).

Measurements BLQ will be imputed with half of the LLOQ for the purpose of calculating change from Baseline. Measurements ALQ, if applicable, will be imputed to the upper limit of quantification.

Cytokines results will be listed.

10.4.3 Serum immunoglobulin concentrations

Immunoglobulins (IgE, IgA and IgM) will be summarized by treatment group and visit for absolute values, change from Baseline, and percentage change from Baseline.

Measurements BLQ will be imputed with half of the LLOQ for the purpose of calculating change from Baseline. Measurements ALQ, if applicable, will be imputed to the upper limit of quantification.

Immunoglobulins (IgE, IgA, and IgM) will be listed.

10.4.4 Anti-tetanus toxoid serum titers

Anti-tetanus toxoid serum titers will be summarized by treatment group and visit for both absolute values, change from Baseline, and percentage change from Baseline. Same summary will be repeated excluding all participants with undetectable baseline titers.

The mean change from Baseline in anti-tetanus toxoid serum titers versus time at each scheduled timepoint will be plotted by treatment group excluding all participants with undetectable baseline titers. Mean change from Baseline in IgG values will be overlaid on the same plot.

Measurements BLQ will be imputed with half of the LLOQ for the purpose of calculating change from Baseline. Measurements ALQ, if applicable, will be imputed to the upper limit of quantification.

Anti-tetanus toxoid serum titers will be listed.

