To assess the pharmacodynamic effects of rozanolixizumab as measured by IgG levels, IgG subclasses, and MG-specific autoantibodies levels	
 • Change from baseline in total IgG and IgG subclasses autoantibodies at each scheduled visit • Change from baseline in MG-specific autoantibodies at each scheduled visit
To evaluate the incidence and emergence of ADAs with respect to immunogenicity, PK, and pharmacodynamics	
 • ADAs at each scheduled assessment during the Treatment Period and Observation Periods
To assess the effect of rozanolixizumab on biomarkers including IgM, IgA, and IgE, serum and plasma complement levels, and serum cytokines	
 • Change from Baseline in serum complement levels (C3 and C4) and plasma complement levels (C3a and C5a) at each scheduled assessment during Treatment Period^a • Change from Baseline in serum cytokines at each scheduled assessment during Treatment and Observation Periods^a • Change from Baseline in serum immunoglobulin concentrations (total IgA, IgE, and IgM) at each scheduled assessment during Treatment and Observation Periods
To assess the effect of rozanolixizumab on tetanus IgG antibodies	
 • Change from Baseline in anti-tetanus toxoid serum titers at each scheduled assessment during Treatment and Observation Period

ADA=anti-drug antibody; ADL=activities of daily living; AESM=adverse event of special monitoring; ECG=electrocardiogram; Ig=immunoglobulin; IVIg=intravenous infusion of immunoglobulin G; MG=myasthenia gravis; MG-ADL=myasthenia gravis-activities of daily living; MGII=myasthenia gravis impairment index; MGQoL15r=revised 15-item myasthenia gravis quality of life questionnaire; PEX=plasma exchange; PK=pharmacokinetic; PRO=patient-reported outcome; QMG=quantitative myasthenia gravis test; SC=subcutaneous(ly); TEAE=treatment-emergent adverse event

^a To be performed for study participants with severe and/or serious headache and/or infusion reaction or hypersensitivity reaction. Other exploratory safety biomarkers may be assessed.

Estimands

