5.2 Exclusion criteria

For criteria pertaining to laboratory measures, the last value from MG0003 or MGC003 will be used for evaluation of study participant eligibility, as long as the measurement was taken within the last 4 weeks (not older than 32 days) prior to MG0004 screening.

Unless otherwise stated, each criterion is applicable to the Screening visit (Visit 1). Participants are excluded from the study if any of the following criteria apply:

Medical conditions

1. Participant has any medical or psychiatric condition that, in the opinion of the Investigator, could jeopardize or would compromise the study participant's ability to participate in this study.
- 2a. Participant has a history of use disorder or other substance use disorder (as per Diagnostic and Statistical Manual of Mental Disorders-5) within the previous 12 months.
3. Participant has a known hypersensitivity to any components of the study medication.
- 4a. Evidence of active or latent tuberculosis (TB) as documented by medical history and examination, if applicable, chest X-rays (posterior anterior and lateral), and TB testing by a positive (not indeterminate) QuantiFERON®-TB Gold Plus.

Prior/Concomitant therapy

5. Participant has received a live vaccination within 8 weeks prior to the Baseline visit; or intends to have a live vaccination during the course of the study or within 8 weeks following the final dose of study medication.

Prior/Concurrent clinical study experience

6. Study participant has experienced hypersensitivity reaction after exposure to other anti-FcRn drugs.

Diagnostic assessments

7. Study participant with severe (defined as Grade 3 on the MG-ADL scale) weakness affecting oropharyngeal or respiratory muscles, or who has myasthenic crisis or impending crisis.
8. Participant has absolute neutrophil count <1500 cells/mm³.
9. Participant has any laboratory abnormality that, in the opinion of the Investigator, is clinically significant, has not resolved at randomization, and could jeopardize or compromise the study participant's ability to participate in this study.
10. Participant has 12-lead electrocardiogram (ECG) with findings considered to be clinically significant upon medical review. The clinical significance of the findings needs to be

assessed by the Investigator to determine eligibility, and any queries regarding continuation of the study participant must be addressed with the Medical Monitor.

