
^a eGFR is calculated using the Chronic Kidney Disease Epidemiology Collaboration (CKD-EPI) formula which is $eGFR = 141 * \min(Scr/\kappa, 1)^\alpha * \max(Scr/\kappa, 1)^{-1.209} * 0.993^{Age} * 1.018$ [if female] * 1.159 [if black]; where Scr is serum creatinine (mg/dL), κ is 0.7 for females and 0.9 for males, α is -0.329 for females and -0.411 for males, min indicates the minimum of Scr/κ or 1, and max indicates the maximum of Scr/κ or 1. If race is not captured, participant will be assumed not Black in the calculation.
 
^b Local urine testing will be standard for the protocol unless serum testing is required by local regulation or Institutional Review Board (IRB)/ Independent Ethics Committee (IEC).
	

Chemistry, hematology and quantitative urinalysis (observed value, absolute change from Baseline) will be summarized in standard unit using descriptive statistics by most recent dose received and RLZ total at each scheduled visit.

The central lab data will be used for the summary tables. Repeated lab measurements will be handled per [Section 4.3](#).

Measurements below the lower limit of quantification (BLQ) will be imputed with half of the lower limit of quantification (LLOQ), and measurements above the upper limit of quantification (ALQ) will be imputed to the upper quantification limit for the purpose of quantitative summaries.

The number and percentage of participants who meet each of the markedly abnormal (MA) criteria outlined in [Section 13.7](#) will be summarized by most recent dose received at any visit (including unscheduled visit).

The laboratory variables that are categorized as normal, high or low based on the reference range supplied by the analytical laboratory will be presented in shift tables from Baseline to any post-Baseline visit (including unscheduled visit) by most recent dose received.

All central or local laboratory test results will be listed, including Baseline, scheduled and unscheduled visits with results in standard unit. Values outside the reference range for the continuous variables will be flagged in the listings. The reference ranges will also be reported in the listings. In addition, the listings will include a flag for values identified as MA. Additional lab test, including pregnancy testing, will also be listed.

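### The anti-tetanus figure plots arithmetic mean absolute change and has no rule for titres taken after a tetanus-containing vaccine or IVIg/PEX rescue, so it can mask the drug's effect

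*SAP*

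**What the plan says.** The protocol lists this aim among its Other objectives: "To assess the effect of rozanolixizumab on tetanus IgG antibodies". SAP 10.4.4 gives the tables: "Anti-tetanus toxoid serum titers will be summarized by treatment group and visit for both absolute values, change from Baseline, and percentage change from Baseline". They are then repeated without participants whose Baseline titre is undetectable. The figure makes the same exclusion: "The mean change from Baseline in anti-tetanus toxoid serum titers versus time at each scheduled timepoint will be plotted by treatment group". Of total IgG, the SAP adds: "Mean change from Baseline in IgG values will be overlaid on the same plot".

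High values have a cap: "Measurements ALQ, if applicable, will be imputed to the upper limit of quantification". Values below quantification are set to half the lower limit, but the sentence ties this to calculating change from Baseline. In SAP 8.3 the same substitution is made "for the purpose of quantitative summaries".

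On vaccination, exclusion criterion 5 (Protocol 5.2) covers recent live vaccination and anyone who "intends to have a live vaccination during the course of the study or within 8 weeks following the final dose of study medication". The prohibited treatments in Protocol 6.5.2 name no vaccine or toxoid. Protocol 6.5.3 provides IVIg or PEX as rescue. SAP 10.4.4 says nothing about titres taken after any of these.

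**The concern.** The objective concerns what rozanolixizumab does to tetanus antibody. A rise caused by a booster is not that effect, nor is a shift caused by IVIg or PEX, which the Protocol's Introduction groups with treatments that act on circulating IgG. The plan keeps all such titres in an arithmetic mean of a quantity in which one participant can rise several-fold while nobody can fall by more than 100%.

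The scale adds a second difficulty. The tetanus curve is in titre units and the IgG curve in concentration units. Participants with high Baseline titres weigh most in a mean absolute change. The overlay therefore cannot show whether tetanus IgG falls in proportion to total IgG, which is the natural reason to draw it. Elsewhere the SAP uses log or ratio scales: ADA titres on a log scale (10.3.2), geometric means for drug concentration (10.1) and percentage change for total IgG (10.2.1).

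Protocol 2.3 lists possible effects on immunizations among the risks, and tetanus is the one vaccine antibody that the SAP analyses. A figure showing little loss could be read as reassurance.

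**Working it through.** The plan has no figure to reproduce: there is no sample size calculation (SAP 2.4) and no testing (SAP 4.1). The check is a break-even calculation.

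**Inputs from the documents.** The maximum size is 240 (SAP 3.9), randomized 1:1, so at most 240/2 = 120 per arm. The only guide to the size of the fall is a reduction of about 70% in total IgG at nadir in the Phase 2 study (Protocol 4.3). That is not a tetanus result, so I use it as the top of an assumed 30% to 70% range.

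**Assumed, not in the documents.** The number boosted, and a post-booster titre of K times the arm's mean Baseline. The cap at the upper limit of quantification is ignored because that limit is not given.

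**Formula.** Scale mean Baseline to 1. Unboosted participants fall by d, and a share f is boosted to K, with average Baseline titres in both groups.

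Mean change = -(1 - f)d + f(K - 1), which is zero at f = d/(d + K - 1).

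For d = 0.5: K = 10 gives 0.5/9.5 = 5.3%, and K = 5 gives 0.5/4.5 = 11.1%.

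Each cell shows the break-even share, then the smallest number of boosted participants that turns the mean positive in an arm of 120 and in an arm of 30.

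| Fall d | K = 5 | K = 10 | K = 20 |
|---|---|---|---|
| 30% | 7.0%; 9; 3 | 3.2%; 4; 1 | 1.6%; 2; 1 |
| 50% | 11.1%; 14; 4 | 5.3%; 7; 2 | 2.6%; 4; 1 |
| 70% | 14.9%; 18; 5 | 7.2%; 9; 3 | 3.6%; 5; 2 |

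**Which statistics are exposed.** This was simulated with 4000 runs, 60 per arm, log-normal Baseline with log-SD 1.0, a true fall of 50%, and 3 participants boosted to about 10 times mean Baseline. All of these values are assumed.

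| Statistic | No boosters | 3 boosted, kept |
|---|---|---|
| Mean change (mean Baseline = 1) | -0.49 | +0.01 |
| Mean % change | -49% | +91% |
| Median change | -0.29 | -0.28 |
| Median % change | -50% | -49% |
| Geometric mean ratio | 0.50 | 0.60 |

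The mean change was zero or above in 53% of runs. The formula alone gives (57 × -0.5 + 3 × 9)/60 = -0.025. The simulation is slightly higher because of its spread. With log-SD 0.3 the boosted mean is 10 × exp(0.045) = 10.46, and with log-SD 0.2 the unboosted mean fall is 1 - 0.5 × exp(0.02) = 0.49. Then 0.05 × 9.46 - 0.95 × 0.49 is about +0.01.

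The geometric mean ratio resists boosters far better than the mean but still moves, so a change of scale does not remove the need for a repeat without those titres. Titres after IVIg or PEX are not modelled and could move in either direction.

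**The case against.** Several points on the other side stand.

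- **Much is already visible.** SAP 3.1 puts median, minimum and maximum beside every mean, titres are listed, and percentage change is tabulated for both tetanus and total IgG. A reader might infer that the loss would be hidden throughout. It would not be: in the simulation the medians barely moved.
- **Leverage is limited.** The cap restrains a boosted titre by an unknown amount. In a full arm with a 50% fall, reversal takes 7 participants at 10 times mean Baseline or 14 at 5 times. That a handful would reverse the curve follows only for large assumed rises or small arms.
- **Sampling is sparse.** The Schedule of Activities has titres every 6 months within Weeks 9 to 48 and at Week 60, and none at Week 52 or PEOT. Week 60 comes 8 weeks after treatment ends, the time in which Protocol 4.2 expects antibodies to return to Baseline, so the assumed fall applies only to on-treatment samples. Rollover to MG0007 through PEOT can shrink the later denominators, which raises leverage.
- **Boosters are not mentioned.** The most that can be said is that they are not named as prohibited. A reader might count a toxoid among the prohibited biologics, but the separate criterion for live vaccines suggests otherwise, and 10.4.4 would keep the titre either way.
- **Treatment policy is the stated approach** (Protocol 3, Estimands). That argues against deleting post-vaccine titres from the main summary. Vaccination is not among the main intercurrent events named, so this does not rule out a companion display.

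A further stronger reading concerns values below quantification. From the narrower wording in 10.4.4, a reader might infer that such titres drop out of the absolute-value means and so conceal antibody loss. No section says so. Repeating the summary without undetectable Baselines implies that those participants are in the main one. The wording needs clarifying; it is not evidence of lost data.

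**Conclusion.** The point holds in a limited form. SAP 10.4.4 rests its figure on arithmetic mean absolute change, overlays a quantity in other units, and has no rule for titres after a tetanus-containing vaccine, IVIg or PEX. The exposed outputs are the figure, the mean column and, most strongly, the mean percentage change.

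The size cannot be determined from the documents. The break-even shares of about 5% (10 times mean Baseline) and 11% (5 times) rest on an assumed 50% fall, average Baseline titres among those boosted, and no effect of the cap. They show that masking is possible, not that it is expected. The endpoint is descriptive and in the Other tier, so no test or decision rule depends on it.

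**What to change.** In SAP 10.4.4:

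1. Tabulate and plot the geometric mean ratio to Baseline for tetanus titre, with total IgG on the same ratio scale.
2. Keep the all-data summary. Repeat the table and plot without titres taken after a recorded tetanus-containing vaccine, tetanus immunoglobulin, IVIg or PEX, and flag those titres in the listing. Concomitant medications and procedures are collected at every visit, and SAP 6.4 already identifies rescue use, so no new data are needed.
3. As a clarification, state that half the lower limit of quantification is also used in absolute-value summaries, as in SAP 8.3.

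The cost is a few lines of SAP text, one extra table and one extra plot, with slightly fewer values in the repeat.
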